
Specific Aims and Hypotheses

Specific Aims and Hypotheses

Research Question

Is Chronotherapy effective treatment for nonbipolar depression?

Specific Aim #1: Demonstrate that Chronotherapy is effective treatment for nonbipolar depressive illness after one week of treatment.

Specific Aim #2: Demonstrate that Chronotherapy is effective treatment for nonbipolar depressive illness after six weeks.

Specific Aim #3: Demonstrate that Chronotherapy shifts the biological clock.

Hypothesis #1: Patients assigned Chronotherapy will be more likely to be remitted at week 1 than those assigned alternative treatment.

Hypothesis #2: Patients assigned Chronotherapy will be more likely to be remitted at week 6 than those assigned alternative treatment.

Hypothesis #3: Shift (earlier) of the onset of night-time melatonin secretion levels will be greater in chonotherapy-treated patients than in those receiving alternative treatment.

Description of Subject Population

Sample #1

Specify subject population

nonbipolar depression

Number of completers required to accomplish study aims

60

Projected number of subjects who will be enrolled to obtain required number of completers

75

Age range of subject population

18-65

Gender, Racial and Ethnic Breakdown

We anticipate our study population will consist of roughly:

Females 60%

Hispanics 15%

Race

Caucasian 65%

African-American/Black 15%

Asian 15%

Other/Mixed/Unstated 5%

Description of subject population

As above

Recruitment Procedures

Describe settings where recruitment will occur

Depression Evaluation Service: 3rd Floor New York State Psychiatric Institute, [name]

[name]: [name]

How and by whom will subjects be approached and/or recruited?

We anticipate that most patients will be approached and recruited by the clinician interviewing patients in IRB Protocol #6669R once it has been presumptively determined that all inclusion and no exclusion criteria have been met.

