
alternative treatment (see below for descriptions). Prior to randomization, all patients will declare what time they desire to end up sleeping ("desired sleep time").

Chronotherapy

Patients assigned chronotherapy will determine which night during the ensuing week they will be able to miss a night of sleep ("Wake Night"); their chronotherapy protocol will begin that night. Following their Wake Night, they will be instructed to sleep 8 hours at specific times; their first allowed sleep will be on the evening following their Wake Night starting at six hours prior to their desired sleep onset time. Their second allowed 8 hours of sleep time will be the following night starting three hours prior to their desired sleep onset time. Those whose desired sleep time is within two hours of the times determined by their responses to the Morningness-Eveningness Questionnaire (MEQ) will thereafter be instructed to sleep only at their desired sleep time. Subjects whose desired sleep time is more than two hours earlier than their MEQ derived ideal sleep time will be given instructions to sleep desired minus six and desired minus 3 hours the initial two allowed sleep nights; thereafter their allowed sleep will be later and later in maximal 3 hour increments until allowed sleep coincides with MEQ determined sleep times; thereafter, their allowed sleep will shift half an hour earlier every two-four days (depending on their ability to waken earlier) until their allowed sleep coincides with their desired sleep time. Whichever allowed sleep paradigm is followed, once sleep is at the desired time, their allowed sleep time will remain their desired sleep time thereafter. Patients whose desired sleep time is within two hours of their MEQ-determined ideal sleep time will sit in front of the bright lights wearing clear goggles throughout at their desired wake-up time beginning the morning following their Wake Night. Those whose MEQ-determined ideal sleep time is more than two hours different from their ideal sleep time will initially sit in front of the bright lights at their MEQ-determined ideal wake-up time, also beginning the morning following their Wake Night; as wake-up times shift earlier, time in front of the bright lights will shift with their allowed wake-up time. For the six weeks following randomization, whenever they sit in front of the light box, patients will be instructed to wear clear goggles.

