To date, the longest time from wake-up prior to institution of a "Wake Night" until post-Wake Night allowed sleep has been 42 hours. Should time from prior wake-up to six hours earlier than desired sleep onset time project to more than 42 hours, first allowed sleep time will be shifted earlier so that first allowed sleep time is no more than 42 hours after their previous day's wake-up time. An additional day or days of shifting sleep will be added such that three hour per day increments (likely shorter on the last night) in allowed sleep time ends at their desired sleep time.

Should any patient have difficulty getting to sleep at the assigned time and/or waking at the prescribed time, they will enter a remedial protocol. This protocol will allow such patients to go to sleep when they feel tired and spontaneously waken for two nights, using the bright lights at the time they spontaneously waken (or at the previously assigned time if spontaneous wakening is earlier than the assigned time). The mean go to sleep and wake-up times of these two nights will determine their allowed sleep onset and wake-up times and the resulting wake-up time will be their new time to sit in front of the bright lights. They will then shift their allowed sleep and light use times half hour forward or back as appropriate until they are sleeping at their desired time and using the bright lights at their desired wake-up time. Should they have trouble shifting in half-hour decrements, shorter decrements will be used.

Alternative treatment

Patients randomized to alternative treatment will also be assigned specific allowed 8 hour sleep times and sit in front of the bright lights for half an hour each morning. Patients assigned alternative treatment will NOT miss a night of sleep; that is, they will not have a Wake Night. Their allowed sleep times will start at their MEQ-determined ideal sleep time. Subsequently, allowed sleep will shift in half hour increments or decrements as appropriate until allowed sleep coincides with desired sleep. They will sit in front of the bright lights each morning on waking up. Whenever they sit in front of the light box, they will be instructed to wear the amber goggles. The remedial protocol above will be followed with any patient unable to shift their sleep.

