All randomized subjects on the night they are randomized will collect saliva to later be analyzed for melatonin. They will be given tubes each of which contains a cotton swab with instructions to place a swab in their mouth every half hour (so, nine swabs = over a four hour period), write the date and time each swab was collected on the tube, refrigerate until they bring the vials in at their next visit. This is repeated over a three hour period at approximately one week (patients who have difficulty reaching their intended sleeping time will delay 2nd saliva collection until they reach their desired sleep time). In order to prevent ambient light from preventing melatonin secretion, all subjects will be issued blue-blocking amber goggles with instructions to wear them from an hour prior to start of saliva collection until the last saliva collection on each of the two nights during which saliva is collected.

Independent Evaluation

All study subjects who are randomized will be evaluated by someone who has no idea what their treatment has been, whether treatment has begun or how long treatment has been if currently being treated. These

Independent Evaluations will occur prior to institution of post-randomization procedures (typically on day of randomization), at the end of Week 1 and at the end of Week 6 post-randomization. If possible, this evaluation will be in person, but when in person interviewing is not possible these evaluations will be made by telephone. Independent Evaluators will be instructed not to ask any questions about treatment or where the interviewee is in the study. Participants will be instructed not to say anything to the Independent Evaluator about whether they are in treatment, or if in treatment what that treatment might be.

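### The second saliva series is put off until a struggling patient reaches desired sleep time, so the Hypothesis 3 melatonin measurement is timed by progress after randomization and can fall at different times in the two arms

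*Protocol*

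**What the plan says.** Hypothesis 3 (Protocol, Specific Aims and Hypotheses) reads: "Shift (earlier) of the onset of night-time melatonin secretion levels will be greater in chonotherapy-treated patients than in those receiving alternative treatment". It needs two saliva series per patient. Under Study Procedures, Melatonin, the first is collected on the night of randomization and the second at about one week, with one exception: "patients who have difficulty reaching their intended sleeping time will delay 2nd saliva collection until they reach their desired sleep time".

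How fast a patient reaches desired sleep time depends on the schedule:

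- **Chronotherapy, desired time within two hours of the time given by the Morningness-Eveningness Questionnaire (MEQ).** After two allowed sleeps, at six and then three hours before desired time, patients "will thereafter be instructed to sleep only at their desired sleep time".
- **Chronotherapy, desired time more than two hours earlier than MEQ time.** Sleep is brought later to MEQ time, and "thereafter, their allowed sleep will shift half an hour earlier every two-four days".
- **Alternative treatment.** Sleep starts at MEQ time. "Subsequently, allowed sleep will shift in half hour increments or decrements as appropriate until allowed sleep coincides with desired sleep". No number of nights per step is given.
- **Remedial rule, both arms.** After two nights of free sleep, "They will then shift their allowed sleep and light use times half hour forward or back as appropriate". Again no number of nights is given. The trigger under Chronotherapy is "Should any patient have difficulty getting to sleep at the assigned time and/or waking at the prescribed time, they will enter a remedial protocol". Under Alternative treatment it is "The remedial protocol above will be followed with any patient unable to shift their sleep".

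The SAP covers only the 17-item Hamilton score at week 6 and does not mention melatonin.

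**The concern.** A fixed one-week sample asks how far melatonin onset has moved after a set amount of treatment. Under the exception, a patient whose sleep has not shifted is sampled later, once it has. The time of measurement then depends on an outcome of treatment. Read literally, a patient who never reaches desired time gives no second series.

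This would matter little if delays were equally common and equally long in both arms. Nothing in the plan makes them so. The routes to desired time differ by arm, two of the half-hour schedules have no stated pace, and the remedial trigger is worded differently for each arm. At stake is whether a difference in melatonin shift reflects the treatments or partly reflects when the second sample was taken.

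**Working it through.** The protocol gives no figure to reproduce. The check asks how far the second series could move and whether one arm is always the later.

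**Inputs.** Nights are counted from the first allowed sleep in each arm (night 1). G is the number of hours by which desired time is earlier than MEQ time, and k is the number of nights per half-hour step. The range k = 2 to 4 is the only half-hour pace in the protocol, and it applies to Chronotherapy patients with G above 2. For the Alternative arm and the remedial rule, every k is an assumption, and k = 1 (a step every night) is added as a fast case. About one week is taken as night 7. The distribution of G is not given.

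**Night on which desired time is reached**

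- Alternative: 1 + 2Gk, since G hours take 2G half-hour steps.
- Chronotherapy, G up to 2: night 3 (desired minus 6, desired minus 3, desired).
- Chronotherapy, G = 3: desired minus 6, desired minus 3, desired, then MEQ time on night 4, then six steps. This gives night 4 + 6k.

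| G | Alternative, k = 1 / 2 / 4 | Chronotherapy |
|---|---|---|
| 1 h | 3 / 5 / 9 | 3 |
| 2 h | 5 / 9 / 17 | 3 |
| 3 h | 7 / 13 / 25 | 16 (k = 2) to 28 (k = 4) |

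**Delay past night 7, if the exception is applied**

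- G = 1: Alternative 0, 0 or 9 − 7 = 2 nights; Chronotherapy 0.
- G = 2: Alternative 0, 9 − 7 = 2 or 17 − 7 = 10 nights; Chronotherapy 0.
- G = 3, k = 2 to 4: Alternative 13 − 7 = 6 to 25 − 7 = 18 nights; Chronotherapy 16 − 7 = 9 to 28 − 7 = 21 nights.

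At G = 2 with steps of two nights or more, the Alternative arm is the later. At G = 3 with the same pace in both arms, Chronotherapy is the later by three nights (16 against 13, or 28 against 25). The sign of the imbalance therefore depends on the mix of gaps, which is unknown.

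**Remedial rule.** These patients plainly have difficulty. Suppose the rule is entered after night 1: nights 2 and 3 are free, and night 4 is set L hours later than desired. Desired time is reached on night 4 + 2Lk.

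- L = 1: night 6, 8 or 12 for k = 1, 2 or 4. Delay past night 7: 0, 1 or 5 nights.
- L = 2: night 8, 12 or 20. Delay: 1, 5 or 13 nights.

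**Swabs.** The first series is nine swabs over four hours at half-hour intervals (4 × 2 + 1 = 9). The second lasts three hours, so 3 × 2 + 1 = 7 swabs.

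**Clock.** The first saliva is collected on the night of randomization, but a Chronotherapy patient may choose a Wake Night in the ensuing week. If it falls 0 to 6 nights after randomization, the first allowed sleep comes 1 to 7 nights after it. If Alternative patients start on the randomization night, night 7 in Chronotherapy is 1 to 7 nights further from the baseline saliva.

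**The case against.** The strongest reply is that the exception covers only patients who have difficulty. An Alternative patient part-way through a planned half-hour schedule is not plainly one of them. Read that way, most Alternative patients give saliva at about one week and the delays in the first list disappear for them. That is a fair reading. It leaves the exception in force for patients who do struggle, including those on the remedial rule, and for them the timing still depends on success in shifting.

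A second reply is that sleep logs, activity monitors and the adherence form record what was delivered in each arm. They show when sleep shifted, but cannot supply a week-1 melatonin value that was not collected.

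A third is that a common night counted from the first allowed sleep gives Chronotherapy more days since the baseline saliva, because of the wait for the Wake Night. This stands as a limitation. Counting from the first allowed sleep matches the arms on nights of scheduled sleep, while counting from randomization would match them on elapsed time only. The unequal wait should be recorded and reported.

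Three stronger readings are tempting and are not supported:

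- A reader might infer that the delay pulls the Hypothesis 3 difference toward zero. The three-hour case shows that the later arm can be Chronotherapy, so no direction is established.
- A reader might infer that a clinician who knows the assignment chooses the control arm's pace. The protocol names nobody as setting it. The words left open follow the choice between earlier and later steps and most naturally concern direction.
- A reader might infer that an unstated pace costs remissions at week 1. The documents give neither the distribution of gaps nor any effect of such small shifts on mood. The phase-advance example in the uploaded chronotherapeutics review is five hours.

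**Conclusion.** The point holds for Hypothesis 3 and no further. The second melatonin measurement is taken at a time that depends on success in shifting sleep after randomization, and the delay can differ between arms. In the remedial examples the delay past night 7 runs from 0 to 13 nights. If mid-schedule patients were also treated as having difficulty, it would run from 0 to 21 nights across the gaps worked here. These ranges rest on assumed step lengths and on illustrative gaps of one to three hours. How many patients would be delayed cannot be worked out from the documents, and the direction of the bias is unknown.

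The SAP's week-6 Hamilton comparison does not use saliva and is not affected. This is an inexpensive improvement to a mechanistic aim, not a flaw in the primary comparison.

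**What to change.** In the Melatonin section, replace the delay with one rule for everyone. Take the second series on the seventh night, counting the first allowed sleep in that patient's arm as night 1, whatever sleep timing has been reached, and use that series for Hypothesis 3. A later series at desired sleep time may be kept for delayed patients as a supplementary measure. Record the nights between the two series and report them by arm.

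As a clarification only, state the Alternative arm's step interval, for example the two to four days, depending on ability to waken, already used for some Chronotherapy patients. The remedial procedure itself needs no restriction.

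The cost is a wording change and, where the later series is kept, about seven more swabs per delayed patient with their assay cost, which the protocol already lists among project expenses.

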I was asked by the IRB Subcommittee to explicitly address what happens clinically and scientifically if patients do not adhere to their Wake Night. Falling asleep, for example, when the individual is assigned to remain awake, not logging in at the prescribed times and all other variances from the protocol will not automatically remove the patient from the protocol. To the extent that it is reasonable and possible, the protocol will be continued through Week 6 as if the violation had not occurred. It is difficult to enumerate each and every possible protocol violation with how each would be handled. The principle will be that from the point the violation is noted, the protocol will be resumed as if the violation had not occurred, though some violations might require new assigned sleep times. The only exception would be if the patient objected or it makes no clinical sense; an example of the latter would be if a patient was supposed to sleep from, say, 6 pm until 2 am, instead slept from noon to 8 pm, we would not insist he/she go back to bed til 2 am but would ask the patient to continue their 8 am bright lights and try not to sleep again til 9 pm the following night (assuming those had been the predetermined times for sleep and lights).

Scientifically, we will record protocol violations (see "Protocol Adherence Form") but all analyses will be "intent to treat". That is, once a patient is randomized, he/she is included in all efficacy analyses out to the

point at which there are no more data; missing intermediate data will be estimated by interpolation, missing end data will be estimated by last observation carried forward.

Treatment after six weeks

Following the six weeks post-randomization period, **for reasons best known to the IRB all fecund women not already known to be pregnant will provide a urine to be tested for pregnancy. While we will make the request of all fecund women, we will not deny post-study treatment to any who fail for any or no reason to supply a post-treatment urine sample.** All patients will be offered continued treatment at the DES as determined jointly by patient and DES physician. In general, those who did well with Chronotherapy would have the recommendation they continue a.m. bright lights and regular sleep times, though they could opt for alternative treatment or to discontinue these and see how they do having the back-up of returning to this or instituting different treatment should depressive symptoms return. Those who do well with the alternative protocol will be allowed to continue it, but with the explanation that we think they probably improved for reasons other than something specific about the Alternative Protocol; therefore, they might best see how things go without the a.m. lights, amber goggles and specific sleep times, reverting to these or other standard treatments should symptoms return. Alternative Treatment subjects who do not benefit, will be offered the alternative of Chronotherapy or standard antidepressant medications. Nonresponders to Chronotherapy will be offered standard antidepressant medications.

Prior to beginning treatment and again six weeks after randomization, all patients will be told that light boxes, goggles, and post-study (i.e., beginning six weeks post-randomization) medications are their responsibility and will not be paid for or supplied by the DES or the NYSPI. They will be informed that the light boxes we use in the study cost about \$150. They will receive six months of clinical visits with a DES psychiatrist beginning six weeks after randomization.

You can upload charts or diagrams if any
Flow Chart.22Nov16.pdf

Criteria for Early Discontinuation

Criteria for Early Discontinuation

- 1) patient withdraws consent
- 2) clinician judgment that change in treatment should not wait until end of study (i.e., six week post-randomization evaluation)
- 3) need for hospitalization
- 4) overt suicidality or clinician judgment that overt suicidality is a significant risk prior to six week post-randomization evaluation.

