Ratings and timing of ratings will be identical for all patients. That is, all will complete the same rating scales throughout. In particular, all subjects will log in for 12 hours out of 24 during their initial 24 hours post-randomization, complete daily mood, sleep and energy logs, wear an activity monitor and have call-in interviews daily during the first post-randomization week. All will be interviewed by an independent evaluator blind to treatment assignment at baseline and Weeks 1 and 6, with ratings by their study clinician daily for the first week and weekly thereafter. At week 6, remitters will be recommended to continue bright light and allowed sleep times, although they will be asked to return their light boxes, goggles and activity monitors. Nonremitters will be offered alternative treatment, including Chronotherapy if assigned to the alternative treatment group and standard antidepressants whichever their assigned study treatment. All randomized subjects will continue to be seen at least monthly for six months with continued ratings each month.

Use of Light Boxes

All fecund women will be instructed to stop using the light box should they become pregnant. Also, regardless of group assignment, patients will be instructed to sit about 18 inches from the light box with eyes open but not looking directly at the light; instead they should read or use their computer or other sedentary activity. They should remain 18 inches from the light for 30 minutes. However, should side effects occur (e.g., overstimulation), the time may be decreased. Tolerance of the light box plus continuing depressed mood will trigger the doctor recommending longer light box use in weekly 15 minute increments up to 60 minutes total; first available increment would be at the week 2 visit, decrements can occur at any time.

Melatonin

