** **only for fecund women not already known to be pregnant**

KEY TO ABBREVIATIONS

CGI (Clinical Global Impression) - this is a clinician rated global measure of the patient's over-all psychopathology and improvement over the past week, improvement compared to pre-treatment

HIGH-C (Hypomania Interview Guide including Hyperthymia, Current Assessment Version) - this is a clinician-rated measure of manic/hypomanic symptoms rated over the past week

labs (laboratory examinations) - these include **EKG**, blood and urine; blood is examined for hematology (e.g., whether the patient is anemic) and routine blood chemistry (e.g., whether the patient has problems with their liver, kidney or thyroid); analysis of the urine determines whether there is a kidney

m-CGI - this is identical to the CGI except it measures the past 24 hours

m-HIGH-C - this is identical to the HIGH-C except modified to measure the past 24 hours

m-PGI - this is identical to the PGI except it is rated for the past 24 hours

m-QIDS - this is identical to the QIDS except it omits sleep and weight items and is rated for the past 24 hours

m-SIGH-ADS - this is identical to the SIGH-ADS except sleep and weight items are removed and ratings are for the past 24 hours

MEQ (Morningness-Eveningness Questionnaire) - this is a 19-item patient-rated questionnaire asking the times of the day respondents prefer to eat, sleep and perform various functions, like exercise, test-taking and working; answers indicate the timing of the individual's biological clock

MMSE (Mini-Mental Status Examination) – this is a standard method for evaluating whether someone is cognitively intact or demented

PE - physical examination

PGI (Patient Global Impression)- this is identical to the CGI except patient-rated, asking patients to rate their over-all symptoms over the past week and improvement relative to pre-treatment

QIDS-SR (Quick Inventory of Depressive Symptoms, Self-Rated) - this is a patient-rated 16-item measure of depressive symptoms which has been shown to correlate highly with the clinician-rated 30-item Inventory of Depressive Symptoms

SCID (Structured Clinical Interview for DSM Diagnoses) - this is a standard semi-structured interview enabling assignment of the major clinical diagnoses according to the DSM diagnostic system, both current and life-time

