Analyses were carried out using data obtained from a systematic search of single- or double-blind clinical trials (clinical trials database; Organon, a part of Schering-Plough Corporation, Roseland, N.J.) comparing mirtazapine with active comparators or placebo in patients with MDD. The studies ranged from March 1982 to December 2003. The algorithm for trial selection is provided in Figure 1. Trials were excluded if there were no HAM-D-17 ratings available, no diagnosis of MDD, or if the study was not blinded. Trials were also excluded if HAM-D-17 assessments were not available at week 2, week 4, and at least once beyond week 4.

Patient Population

All patients met DSM-III-R or DSM-IV criteria for the diagnosis of at least 1 major depressive episode. The

HAM-D-17 total score was used to assess the baseline severity of depressive symptoms (mild = < 22; moderate = 22–25; severe = > 25). Each study was approved by the institutional review board for the participating site. Written informed consent was obtained from all participants prior to participation in the original clinical trials and all studies were conducted in compliance with the current revision of the Declaration of Helsinki.

Outcome Measures

For the purpose of this analysis, the following patient groups were defined:

1. Early improvers: patients having a reduction in HAM-D-17 score of $\geq 20\%$ compared with baseline within the first 2 weeks of treatment. This threshold represents a clinically meaningful change in the patient's state and can be reliably assessed.
2. Treatment responders: patients having a reduction in HAM-D-17 score of $\geq 50\%$ from baseline.
3. Stable responders: patients having a reduction in HAM-D-17 score of $\geq 50\%$ from baseline at 4 weeks of treatment and at all subsequent assessments.
4. Symptom remitters: patients having a reduction in HAM-D-17 score to ≤ 7 points.
5. Stable remitters: patients having a reduction in HAM-D-17 score to ≤ 7 points at week 4 of treatment and at all subsequent assessments.

Statistical Analyses

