2.3. Data collection

On the day proceeding total sleep deprivation (Day 0), after participants signed informed consent, we performed a chart review

Table 1
Demographics.

N = 10	
Age	Mean = 44 ± 16.4 SD
Gender	4 Male, 6 Female
Race/Ethnicity	9 (90%) Caucasian 1 (10%) African American
Duration of current episode	15.4months ± 13.2 SD
Number of lifetime episodes	7.8 ± 5.8 SD
Number of failed medications/ECT	5.5 ± 5.7 SD One failure of ECT

as well as reviewed pertinent laboratory testing. We then performed a MINI neuropsychiatric examination (Sheehan et al., 1998) to confirm diagnoses, administered a 17-Item Hamilton depression rating scale (HAM17) (Hamilton, 1960), Columbia Suicide Severity Rating Scale (CSSRS) (Posner et al., 2011), and a Young Mania Rating scale (YMRS) (Young et al., 1978), inquiring about the previous 7 days. In addition, we collected self report measures at baseline, including the Inventory of Depressive Symptoms Self Report (IDS-SR) (Rush et al., 1996), the Patient Health Questionnaire-9 (PHQ9) (Spitzer et al., 1999), the Epworth Sleepiness scale (ESS) (Johns, 1993), the Pittsburgh Sleep Quality Index (PSQI) (Buysse et al., 1989), and the Scale for Suicidal Ideation (SSI) (Beck et al., 1979). On the day following total sleep deprivation, and the days following the first two nights of sleep phase advance (Days 1–3), we administered the 6-item version of the Hamilton Depression Rating Scale (HAM-D6) (O'Sullivan et al., 1997), the CSSRS, the YMRS, the IDS-SR, the ESS, and the SSI all asking about the previous day only. On the day following the third sleep phase advance night (Day4), we administered the HAM17, CSSRS, and YMRS, and collected the IDS-SR, ESS, SSI, PHQ9, and PSQI asking about the previous day only. We defined remission from depression as a HAM17 score of less than 7. We defined response from either depression (HAM17), or suicidal ideation (CSSRS) as a greater than 50% drop in score from baseline.

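### Interpolating a missed week-1 evaluator score would class nearly every such patient as non-remitted, which works against the rapid-remission question in Hypothesis 1

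*Protocol*

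**What the plan says.** - **Hypothesis 1** (Protocol, Specific Aims and Hypotheses): "Patients assigned Chronotherapy will be more likely to be remitted at week 1 than those assigned alternative treatment". No rater, scale or remission cutoff is given.
- **Who rates when** (Protocol, Study Procedures, after the description of the alternative treatment): "All will be interviewed by an independent evaluator blind to treatment assignment at baseline and Weeks 1 and 6". The treating clinician follows a denser schedule, described there as "with ratings by their study clinician daily for the first week and weekly thereafter". The Flow Chart agrees. The evaluator's SIGH-ADS falls at randomisation, D7 and W6. The clinician's full SIGH-ADS falls at randomisation, D7 and W2 onwards, and the shortened m-SIGH-ADS runs daily from randomisation to D7. The Key to Abbreviations says of the shortened form: "this is identical to the SIGH-ADS except sleep and weight items are removed and ratings are for the past 24 hours".
- **Missing data** (Protocol, Protocol Violations): every randomised patient stays in the efficacy analyses, "missing intermediate data will be estimated by interpolation", and "missing end data will be estimated by last observation carried forward". The text does not say whether interpolation is linear, which rating series supplies the neighbouring values, or whether it applies to the score or to remission status.
- **Severity at entry** (Protocol, Inclusion/Exclusion Criteria): entry is by diagnosis, with no minimum Hamilton score.
- **SAP**: its only analysis is a t-test of the evaluator's HAM-D17 score at week 6. It has no missing-data rule and no analysis of Hypothesis 1.

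**The concern.** Week 1 is the only intermediate visit in the evaluator's series, so its only neighbours there are baseline and week 6. A straight line between two points six weeks apart assumes slow, even improvement. Hypothesis 1 asks whether improvement comes as a step within days. The filling rule therefore assumes the opposite of what is being tested, and it uses a later score to set an earlier endpoint.

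A Chronotherapy patient who was well from the first days through week 6, but missed the week-1 interview, would be counted as still depressed at week 1. If missed week-1 interviews were more common in one arm, the error would be larger in that arm. That is conceivable, because only one arm loses a night of sleep around that time, but the documents give no missing-visit rates.

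**Working it through.** The documents give no figure that depends on the interpolation rule, so there is nothing of the plan's to reproduce first.

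**Inputs.** B is the baseline score, and W1, W2 and W6 are the scores at weeks 1, 2 and 6. The cutoff is an assumption taken from the reprinted meta-analysis of antidepressant trials: "Symptom remitters: patients having a reduction in HAM-D-17 score to ≤ 7 points". The reprinted inpatient chronotherapy pilot differs slightly: "We defined remission from depression as a HAM17 score of less than 7". The week-1 remission rate is the team's own open pilot result, 10/18 = 56%, with stated limits of 31-78% (Background, Significance and Rationale).

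**1. Evaluator series, linear.** W1 = B + (W6 - B)/6 = (5B + W6)/6. A value of 7 or lower needs 5B + W6 ≤ 42, so B ≤ 42/5 = 8.4 even when W6 = 0. On whole-number baselines:

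| B | W6 = 0 | W6 = 3 | W6 = 7 |
|---|---|---|---|
| 8 | 6.67 | 7.17 | 7.83 |
| 9 | 7.50 | 8.00 | 8.67 |
| 16.3 | 13.58 | 14.08 | 14.75 |
| 24.7 | 20.58 | 21.08 | 21.75 |

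Non-remission is certain from B = 9. If the stricter cutoff is read as 6 or lower, the condition is 5B + W6 ≤ 36, so B ≤ 7.2 and non-remission is certain from B = 8. The last two rows use mean baselines from the reprinted seasonal-depression study and the inpatient pilot (SD 4.2 in both). On a normal approximation, the share with B ≤ 8 is about 3% and below 0.1% respectively.

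**2. Full-scale clinician series.** The neighbours of D7 are randomisation and W2, so the filled value is the midpoint (B + W2)/2. A value of 7 or lower needs B ≤ 14 even when W2 = 0. Non-remission is certain from B = 15.

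**3. No later evaluator rating.** The end-data rule carries the evaluator's baseline forward, so week 1 equals B. That is non-remission for any B above 7.

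**4. Effect on the rates.** Let m be the share with a filled week-1 value, unrelated to true remission within the arm, and treat every filled value as non-remitted. The observed rate is p(1 - m). From 56%: 0.56 × 0.95 = 53.2%, 0.56 × 0.90 = 50.4%, 0.56 × 0.80 = 44.8%. From the unrounded 10/18, the last is 44.4%. The values of m are assumptions.

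**5. Effect on the comparison, equal m.** The difference becomes (p1 - p2)(1 - m). For illustration, p2 = 4.7%, the day-8 comparator remission in the reprinted wake-therapy trial (a six-item scale, with patients on medication). Power is for 30 per arm (target 60, 1:1 assumed), two-sided 5%, normal approximation.

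| p1 vs p2 | m | Difference (points) | Power |
|---|---|---|---|
| 56% vs 4.7% | 0 / 5 / 10 / 20% | 51.3 / 48.7 / 46.2 / 41.0 | 99.8 / 99.6 / 99.2 / 97.7% |
| 31% vs 4.7% | 0 / 5 / 10 / 20% | 26.3 / 25.0 / 23.7 / 21.0 | 77 / 74 / 72 / 65% |

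**6. Unequal m.** The difference is p1(1 - m1) - p2(1 - m2). With 56% vs 4.7% and 20% missing in Chronotherapy only: 44.8 - 4.7 = 40.1 points. With 20% missing in the comparator only: 56 - 3.8 = 52.2 points, slightly above the true 51.3.

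**The case against.** A reader might infer that every missed week-1 rating is bound to become non-remission, and that everyone who misses week 1 and returns later is mis-scored. The documents do not support that.

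- **The result is conditional.** Linear form, the evaluator series, filling at score level and the cutoff of 7 are all unstated. With no minimum severity, B = 8 and W6 = 0 gives 6.67, a remission.
- **A denser series exists.** If the daily clinician ratings supplied the neighbours, D6 = 4 and W2 = 6 would give 4 + (6 - 4)/8 = 4.25, a remission. That mixes a shortened 24-hour scale with the full one, so it is not a HAM-D17 score, but it shows that the daily data are informative about week 1.
- **Only true remitters are mis-scored.** A non-remitter filled as non-remitted is scored correctly. On the illustrative rates, about 56% of the missing Chronotherapy patients and about 5% of the missing comparator patients would be affected.
- **Interpolation is not the only cause.** Baseline carry-forward makes the same error, so removing interpolation alone would not be enough.
- **Missed interviews may be few.** The sections on Independent Evaluation and Telephone Visits already allow telephone ratings.

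All of this limits the point, and none of it removes it. The interpolation rule is stated, it covers the efficacy analyses, and both full-scale readings work against early remission. Two distant points carry no information on when the improvement occurred, so any other curve would need an assumption that the plan does not supply.

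**Conclusion.** The point holds in conditional form. Under linear interpolation of evaluator scores and a cutoff of 7, every missing week-1 score with a baseline of 9 or more becomes non-remission. The full-scale clinician midpoint does the same from 15, and baseline carry-forward does so above 7. Patients truly remitted at week 1 are then mis-scored for Hypothesis 1.

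With equal missingness the consequence is attenuation by the factor (1 - m). Power barely moves at the pilot's 56%, and falls from 77% to 65% at its lower limit of 31% with 20% missing, against the illustrative comparator. Unequal missingness could bias the comparison in either direction. The missing shares, comparator rate, cutoff and two-sided test are assumptions.

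Two further inferences should be resisted. The SAP's week-6 t-test does not use the week-1 score, so this rule does not affect it. Nor does the rule by itself manufacture an apparent benefit: with equal missingness it shrinks the difference.

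**What to change.** For the week-1 remission endpoint, replace both interpolation and baseline carry-forward with multiple imputation of the evaluator's HAM-D17 score from arm, baseline and the daily clinician ratings of days 1-7. Use those ratings as predictors, not as HAM-D17 scores, because the scale and time window differ. Keep arm in the model, since the protocol does not describe the treating clinician as blinded. Report one sensitivity analysis that counts missing as non-remitted in both arms. This is close to what the current rule would give under the linear evaluator reading, so that result is still reported.

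In the same edit, name the rater and the remission cutoff for Hypothesis 1, and put both in the SAP.

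The cost is a few sentences in Protocol Violations and the SAP, and slightly more analysis work. The predictors are already on the Flow Chart, so no new visits or staff are needed. Multiple imputation assumes that missingness is explained by the variables in the model, which is why the sensitivity analysis should accompany it.
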